#### **9.3.2 Assessing the Cleansing of the Transverse Colon**

The responder rate for the transverse colon using BBPS will be analysed in the same manner as the primary endpoint for the mITT analysis set, according to the subjects’ randomized treatment group, and 95% confidence interval for the responder rate of NaP/MC Oral Solution minus PREPOPIK® will be presented. A subject is considered to be a “responder” if the BBPS score of the transverse colon is  $\geq 2$ .

#### **9.3.3 Assessing the Cleansing of the Left Colon**

The responder rate for the left colon using BBPS will be analysed in the same manner as the primary endpoint for the mITT analysis set according to the subjects’ randomized treatment group, and 95% confidence interval for the responder rate of NaP/MC Oral Solution minus PREPOPIK® will be presented. A subject is considered to be a “responder” if the BBPS score of the left colon is  $\geq 2$ .

#### **9.3.4 Tolerability and Satisfaction**

For Mayo Clinic Bowel Prep Tolerability Questionnaire (see [Appendix 4](#) ), each question will be analysed separately and summary statistics will be provided for all individual questions by randomized treatment group for the mITT population. The Wilcoxon Rank Sum 2-sided test will be used for the treatment comparison of ordered categorical responses. In contrast, for binary responses Fisher’s exact test will be utilized.

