4.2.2 Randomization

The randomization list will be generated by an independent, unblinded statistician prior to the first subject's first visit. Each subject will be randomized (1:1) to one of the two treatment arms, NaP/MC Oral Solution or PREPOPIK[®], prior to the distribution of study drug. Randomization numbers will be

allocated sequentially to the subjects at each site, in the order in which the subjects are randomized at the site.

A subset of subjects will participate in a PK assessment and will have blood samples collected four times on the day that the colonoscopy is performed. Approximately 60 randomized subjects will be included in this PK sub-group. A subset of sites will be identified as PK sites and subjects for this sub-group will come from these sites. Randomization will be stratified by site and PK sub-group (whether or not a subject participates in the PK sub-group).

Under no circumstances will subjects enrolled in the study be permitted to re-enroll for a second time in this study.

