9.6.3.4 Tolerability and Satisfaction

Mayo Clinic Bowel Prep Tolerability Questionnaire (see [Appendix D](#)) questions 2, 3, 4, 6 (for each category), and 9 will be analyzed separately and summary statistics will be provided for all individual questions by randomized treatment group for the mITT population. The Wilcoxon Rank Sum 2-sided test will be used for the treatment comparison of ordered categorical variables.

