#### 9.2.1 Primary Variable(s) Analysis

For primary analysis what is of interest is the assessment of the difference in responder rates in overall colon cleansing between NaP/MC Oral Solution and PREPOPIK®. A subject is considered to be a “responder” if overall colon cleansing is classified as either “excellent” or “good” by the blinded endoscopist using the Modified Aronchick Scale (see [Appendix 3](#) ). The NI margin for the difference between treatments (NaP/MC Oral Solution minus PREPOPIK®) will be -8% (absolute). The NI hypothesis to be tested for the primary endpoint will be:

$$H_0: \pi_{\text{NaP/MC Oral Solution}} - \pi_{\text{PREPOPIK}^{\circledR}} \leq -8\%$$

against the alternative

$$H_1: \pi_{\text{NaP/MC Oral Solution}} - \pi_{\text{PREPOPIK}^{\circledR}} > -8\%,$$

where  $\pi_{\text{NaP/MC Oral Solution}}$  and  $\pi_{\text{PREPOPIK}^{\circledR}}$  denote the true percentage of subjects classified as responders (i.e., excellent and good according to the Modified Aronchick Scale (see [Appendix 3](#) )) among subjects treated with NaP/MC Oral Solution or PREPOPIK®, respectively, for colon cleansing in preparation for colonoscopy.

The null hypothesis ( $H_0$ ) will be tested against the alternative by constructing a 2-sided 95% confidence interval for the difference in responder rates. The primary analysis will be stratified by the stratification factor, site, by using the Mantel-Haenszel method to combine results across sites. In brief, this corresponds to deriving a weighted average across sites where the weight depends on the number of observations in each treatment group in each stratum (see [Appendix 2](#) for more details). Subjects who do not have an excellent or good rating according to the Modified Aronchick Scale (see [Appendix 3](#)) for any reason will be considered treatment failures (i.e., not a responder). Hence, treated patients that did not complete the colonoscopy assessment will be classified as non-responders. If the lower limit of the 95% confidence interval is greater than the margin (-8%), the null hypothesis will be rejected and it will be claimed that NaP/MC Oral Solution is non-inferior to PREPOPIK® with respect to colon cleansing in preparation for colonoscopy.

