## Appendix 4 Mayo Clinic Bowel Prep Tolerability Questionnaire

Mayo Clinic Bowel Prep Tolerability Questionnaire	

• Please, fill this questionnaire the morning of your colonoscopy procedure

• Please mark (for example ✓) the most appropriate response according to your current experience with the bowel preparation.

• Please, return this questionnaire at the front desk in the Gastroenterology department when you check-in for your procedure.

	

Patient name: \_\_\_\_\_

Age: \_\_\_\_\_

Gender:  Male  Female

Bowel prep: \_\_\_\_\_

Regimen:  PM only (single dose)  PM/AM (split dose)

1. How many bowel movements did you have in the week prior to starting colon preparation?

- 3 or less/week
- 4 to 8/week
- 9 or more/week

2. How much of the bowel preparation solution was left in the bottle after drinking it to your best effort?

- Less than 25%
- 25% - 50% left
- 50% - 75% left
- 75% or more left

3. How tolerable did you find the bowel preparation?

- Easy
- Acceptable
- Somewhat difficult
- Very difficult
- Unacceptable

4. Based on your current experience, would you be willing to drink the same preparation again if you need another colonoscopy in the future?

- Not willing at all
- Somewhat willing
- Mostly willing

5. In case you have experienced some difficulties in tolerating the bowel preparation, do you think that was due to your current health issues? (Check more than 1 option if applicable)

- Yes
- No
- It does not apply to me (I did not have any difficulties tolerating bowel preparation)
- It does not apply to me (I do not have any health issues)

©2014 Mayo Foundation for Medical Education and Research. All rights reserved. MCI7410

6. How much the following symptoms bothered you during bowel preparation?

Symptoms	None	Mild	Moderate	Severe
Bad taste in your mouth	1	2	3	4
Gastric fullness	1	2	3	4
Lack of sleep from excessive bathroom trips	1	2	3	4
Nausea/vomiting	1	2	3	4
Bloating/abdominal distention/gas	1	2	3	4
Abdominal pain/cramps	1	2	3	4
Headache	1	2	3	4

Others (please specify the symptom (s) and indicate how bothersome it was):  
\_\_\_\_\_  
\_\_\_\_\_

7. Is this your first colonoscopy procedure?

- No (please, answer the following questions)
- Yes (end of the questionnaire)

8. Which type of bowel preparation did you take in your previous colonoscopy?

- GoLyteley (1 gallon tasteless/salty solution)
- Moviprep (1/2 gallon flavored solution)

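### Tolerability answers are compared without the site stratification used for the responder endpoints, and the SAP widens the protocol's list of analysed questions without declaring it

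*SAP*

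**What the plan says.** **Allocation.** Protocol 4.2.2: "Randomization will be stratified by site and PK sub-group".

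**Responder endpoints.** SAP 9.2.1: "The primary analysis will be stratified by the stratification factor, site, by using the Mantel-Haenszel method to combine results across sites". SAP 9.3.1 to 9.3.3 apply the same method to the right, transverse and left colon.

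**Tolerability test.** SAP 9.3.4, for ordered answers: "The Wilcoxon Rank Sum 2-sided test will be used for the treatment comparison of ordered categorical responses". For two-category answers it adds: "for binary responses Fisher’s exact test will be utilized". Neither is stratified. Protocol 9.6.3.4 also names a plain Wilcoxon rank sum test, so the unstratified test is not new in the SAP; the Fisher test is.

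**Questions covered.** Protocol 9.6.3.4: "questions 2, 3, 4, 6 (for each category), and 9 will be analyzed separately". SAP 9.3.4: "each question will be analysed separately and summary statistics will be provided for all individual questions by randomized treatment group for the mITT population". SAP section 12, which records departures from the protocol's analysis, says only that the handling of the binary tolerability question was made clearer. It does not mention the wider list.

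**The concern.** There are two separate issues with separate consequences.

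*Stratification.* When arms are balanced within site, variation between sites drops out of the treatment comparison. An unstratified rank test still counts it as noise, so its variance estimate is too large when sites differ. The test then rejects less often than its nominal level and loses some power. The plan avoids this for the responder endpoints but not for tolerability, and gives no reason.

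*Question list.* Question 1 asks about bowel movements in the week before preparation. Question 7 asks "Is this your first colonoscopy procedure". Neither answer can be changed by the assigned product. A small p-value on either would be chance imbalance printed under a tolerability heading. Question 8 (type of previous preparation) has unordered categories and question 5 allows several boxes to be ticked, so neither named test fits them as they stand.

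**Working it through.** **Plan's own figure.** The documents state no power or sample size for tolerability. The stated 450 per arm is for the primary test and is used here only to set the trial's size. It reproduces: (1.960 + 1.282)² × 2 × 0.84 × 0.16 / 0.08² gives 442 per arm, and power at 450 is 90.5%.

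**Inputs from the documents.** About 900 subjects, 1:1, some 10–15 sites (Protocol 3.2); two-sided 5% for each test (SAP 9.1).

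**Inputs assumed.** The tolerability effect, the spread of answers over categories, and the between-site variation. Results are therefore given as a range.

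**Statistics compared.** Within site j, with N_j subjects, let S_j be the centred rank sum of one arm and V_j its tie-corrected variance. Van Elteren refers [Σ S_j/(N_j+1)]² / Σ[V_j/(N_j+1)²] to 3.84. The unstratified test uses S²/V with all subjects ranked together.

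**Simulation 1.** 15 sites × 30 per arm, five-level item, latent shift 0.20 SD, 3,000 replicates.

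| Between-site share of variance | Power, unstratified | Power, van Elteren | Loss (points) | Null rejection, unstratified |
|---|---|---|---|---|
| 5% | 79.4% | 80.4% | 1.0 | 4.7% |
| 10% | 80.0% | 81.9% | 1.9 | 4.1% |
| 20% | 81.3% | 85.1% | 3.8 | 3.1% |

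At 0–2% the two tests agree within 0.5 point. The comparison to read is across each row.

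**Simulation 2.** Proportional-odds model, log odds ratio 0.36, five levels split 40/35/15/7/3%, 2,000 replicates per setting. A site SD of σ on the logit scale corresponds to a variance share of σ²/(σ² + π²/3).

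| Site SD | Share | 10 sites: unstratified v van Elteren | 15 sites: unstratified v van Elteren |
|---|---|---|---|
| 0 | 0% | 82.1% v 82.3% | 82.6% v 82.0% |
| 0.3 | 2.7% | 83.0% v 83.4% | 81.0% v 81.5% |
| 0.5 | 7.1% | 79.3% v 81.5% | 80.5% v 82.0% |
| 0.8 | 16.3% | 75.8% v 80.7% | 75.6% v 81.0% |
| 1.0 | 23.3% | 73.0% v 81.8% | 71.4% v 79.8% |

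A four-level item with 12 sites loses 2.0 points at SD 0.5 and 7.5 at SD 1.0. Under the null with 12 sites (3,000 replicates), the unstratified test rejects 5.8%, 4.4% and 3.3% of the time at SD 0, 0.5 and 1.0; van Elteren rejects 5.8%, 4.8% and 5.2%. The 5.8% shared by both tests at SD 0 is within about two Monte Carlo standard errors of 5% (√(0.05 × 0.95/3,000) = 0.4 point).

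**A further run**, with 1,500 replicates, gave gains from stratifying of 0.8 and 2.4 points at 5% and 10% with equal sites, and 0.4 and 2.6 with unequal sites. Adding PK sub-group to the strata changed the result by no more than 0.3 point.

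**Number of tests.** The protocol's list is questions 2, 3 and 4 (3), seven named symptoms in question 6 (7) and question 9 (1), making 11. Adding questions 1 and 7 makes 13. If all nulls hold and the tests are independent, the chance of at least one p < 0.05 is 1 − 0.95¹¹ = 43.1% for 11 tests and 1 − 0.95¹³ = 48.7% for 13. For questions 1 and 7 alone it is 1 − 0.95² = 9.8%. The seven symptom items come from the same subjects, so independence is a simplification.

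**The case against.** The case for leaving the section alone has real weight.

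- *The test is valid and prespecified.* It is in the protocol, and no document promises site adjustment for tolerability. This stands. A reader might infer that ignoring site inflates false positives; the null rejection rates show the opposite.
- *The power loss is small and rests on assumptions.* This also stands. Tolerability is to be evaluated, not tested against a powered hypothesis, and its endpoint is the frequency of each answer category. The losses of 8–9 points at a site SD of 1.0 need site differences that nothing in the documents suggests.
- *Summarising every question is not new.* Correct: the protocol also promises summary statistics for all individual questions. What changed is which questions are analysed with a test assigned by response type. The SAP does not name questions 1 and 7, and the table shells are in a separate document (SAP section 14), so testing them is the literal reading rather than an explicit instruction.
- *The Fisher test may have another target.* A reader might infer that it can apply only to question 7, a pre-treatment fact. The documents do not establish that. Question 5 has Yes and No boxes and concerns difficulty tolerating the preparation, and section 12 does not say which binary item is meant.
- *Multiplicity is mostly the protocol's own.* True: 11 of the 13 tests remain after the fix. The two extra tests take no power from the others, because no adjustment is applied.

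None of this gives a reason to prefer the unstratified test or explains the undeclared change of list.

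**Conclusion.** The point holds as a minor improvement with two parts.

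1. The unstratified Wilcoxon test is valid but conservative when sites differ. With 5–10% of variance between sites, it costs about 1–2 power points; with no site differences, nothing material. The size depends on assumed site variation, effect and category splits; the direction was the same in all three sets of simulations.
2. SAP 9.3.4 widens the protocol's question list, and section 12 does not say so. This rests on the text alone. Read literally, it adds tests of questions 1 and 7 that can show only chance imbalance.

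A reader might infer that the trial's main claims are weakened. They are not: these tests lie outside the sequence in SAP 9.1, so the primary, right-colon and superiority conclusions are unaffected.

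**What to change.** In SAP 9.3.4:

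- Use the van Elteren test (Wilcoxon stratified by site) for questions 2, 3, 4, each question 6 symptom, and 9. Site alone matches the primary analysis. PK sub-group need not be added: it covers only about 60 subjects from a subset of sites and made no material difference in the check.
- Report questions 1, 5, 7 and 8 descriptively, without tests, and drop the Fisher sentence.
- Label the p-values as nominal.

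In SAP section 12, list the change from the protocol's unstratified test. Once the question list is restored, there is no list change left to declare.

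The cost is a few lines of SAP text and a standard software option, settled before unblinding. Question 9 is answered only by subjects with a previous colonoscopy, so its site strata will be thinner; this was not simulated. If only one change is made, restoring the protocol's list removes the undeclared discrepancy.

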#### **9.3.5 Drug Concentration Measurements/Pharmacokinetics**

Drug concentrations of picosulfate, BHPM and magnesium (which is part of the chemistry lab assessment) will be summarized by descriptive statistics. A population PK model will be developed

based on pooled data from the present study and previous study in adult subjects (000017). Apparent clearance and volume of distribution will be estimated, if possible. The population PK model and other PK endpoints will be summarized in a separate PK modelling report.

#### **9.4 Other Endpoints**

Whether or not colonoscopy was completed, whether or not cecum was reached, the overall colonoscopy evaluation, time taken to reach the cecum, time to withdrawal and number of polyps and histology will be summarized by treatment group. Furthermore, associated listing will be produced. The listing will include information on the histologic details of the polyps and the morphology.

##### **9.4.1 Subgroup analysis**

The primary endpoint will be summarized by age (<65 or  $\geq$  65), gender and site. The analysis outlined for the primary endpoint will be applied to age and gender subgroup analysis. For the by site summary, the proportion of responders will be presented by treatment group. Furthermore, the proportion difference between the treatment groups and associated 95% CI will be generated.

## 10 Safety

### 10.1 General Considerations

Safety parameters will be evaluated for the safety analysis data set according to actual treatment received. No formal statistical hypothesis testing will be conducted for the safety parameters.

### 10.2 Adverse Events

Adverse events (AEs) are classified according to the Dictionary for Regulatory Activities (MedDRA) version 16.1 or later.

A Treatment-emergent adverse event (TEAE) is any adverse event that occurs after the start of IMP and within 30 days from the last exposure to IMP, or a pre-treatment adverse event/medical condition that worsens in intensity after the start of IMP and within 30 days from the last exposure to IMP. The total number of subjects reporting a TEAE, the percentage of subjects (%) with a TEAE, and the number of treatment-emergent adverse Events (E) reported will be presented.

Missing values will be treated as missing, except for causality, intensity, seriousness, and outcome of AE. A ‘worst case’ approach will be used:

- if causality is missing, the AE will be regarded as related to the IMP
- if the intensity of an AE is missing, the AE will be regarded as severe
- if seriousness is missing, the AE will be regarded as serious
- if outcome is missing and no date of outcome is present, the outcome is regarded as ‘Not yet recovered’

Missing event start and event stop dates will be imputed in the most conservative way, i.e. the event should start as early as possible based on the (partially) missing start date while remaining treatment emergent (if relevant), and last as long as possible, i.e. until last visit or one day prior to the next event with the same preferred term, if any. In the latter case both consecutive AEs (with the same PT) will remain to be regarded as two separate events (despite being adjacent). Written narratives will be issued for all serious AEs (including deaths) and AEs leading to withdrawal.

#### 10.2.1 Overview of Treatment-Emergent Adverse Events

An AE overview summary table will be prepared including the number of subjects reporting an AE, the percentage of subjects (%) with an AE, and the number of events (E) reported, for the following categories:

- Treatment-emergent adverse events
- Deaths
- Serious adverse events
- Adverse events leading to withdrawal

- Severe and life threatening adverse events
- Adverse drug reactions

### 10.2.2 Incidence of Adverse Events

Treatment-emergent adverse events will be summarised in a Table by SOC and PT using the latest version of MedDRA. The Table will display the total number of subjects reporting an AE, the percentage of subjects (%) with an AE, and the number of events (E) reported. AEs will be presented by system organ class (SOC) sorted alphabetically and preferred term (PT) sorted in decreasing frequency of occurrence.

Summary tables will be prepared for:

- All TEAEs
- TEAEs with an incidence of  $\geq 5\%$
- Non-serious TEAEs with an incidence of  $\geq 5\%$
- TEAEs by causality (related/unrelated)
- Adverse events leading to death
- TEAEs by intensity
- Serious adverse events
- Adverse events leading to withdrawal

Supporting data listings will be provided for:

- All adverse events sorted by centre and subject no.
- All adverse events sorted by MedDRA Preferred Term
- Serious adverse events
- Adverse events leading to death
- Adverse events leading to withdrawal.

A listing of pre-treatment and post-treatment AEs will be generated. A pre-treatment AE is any AE that ends prior to exposure to IMP. In contrast, a post-treatment IMP is an AE that starts 30 days after IMP exposure. The pre-treatment AE listing will include all patients that signed informed consent. In contrast, the post-treatment AE listing will be limited to the safety population.

### 10.3 Safety Laboratory Variables

Baseline for all laboratory analyses will be the values obtained at the last assessment prior to the first dose of the investigational medicinal product (IMP). Treatment-emergent laboratory data will include tests completed after the first dose of IMP. End of trial assessment will include the last post-baseline observation during the trial.

Laboratory variables will be grouped under “Haematology”, “Clinical Chemistry” or “Urinalysis”

### 10.3.1 Summary Statistics

Observed values and change from baseline values for each visit and for the end of trial (last visit) will be summarized for each laboratory variable by treatment group. The summary will include the number of subjects with data, mean (standard deviation), median, minimum, and maximum values.

### 10.3.2 Laboratory Variable Changes Relative to Normal Range

Changes relative to normal ranges are presented with shift tables with total number of subjects, and number and percent of subjects who experienced a shift by treatment group. The following categories for shift tables are defined:

- Low: Values which are below the lower reference range limit;
- Normal: Values which are within the lower and upper reference range;
- High: Values which are above the upper reference range limit.
- Absent: No value for measured variable (for urinalysis only)
- Present: Any value obtained for measured variable (for urinalysis only)

For all haematology and clinical chemistry variables, shift tables will be prepared to compare baseline values to the worst in-treatment value. More specifically, for haematology and clinical chemistry, tables presenting the changes from *Low* or *Normal* to *High* and from *High* or *Normal* to *Low* will be provided. For urinalysis variables, shift tables will summarise the number (%) of subjects who had “absent” values at baseline and “present” values during the treatment period.

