### 10.3.4 Urinalysis

Categorical urinalysis laboratory data will be summarized separately by treatment group and scheduled time point using the number and percentage of subjects in each category. Furthermore, incidence of changes in urinalysis will be summarised by treatment group. A summary table with number of subjects with change from *Absent* at baseline to *Present* during trial will be summarised.

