## Appendix 1     Markedly Abnormal Laboratory Safety Values, Vital Signs and ECGs

**Table 2: Markedly abnormal Criteria for Laboratory Tests**

Variable	Units	Markedly abnormal Criteria	
		Low	High
Haematology			
Haemoglobin	g/L	$\leq 115$	Not applicable
Haematocrit	Ratio	$\leq 0.37$	$\geq 0.56$
Total WBC	$10^9/L$	$\leq 2.8$	$\geq 16.0$
Eosinophils	%	Not applicable	$\geq 10$
Neutrophils	%	$\leq 15$	$\geq 90$
Lymphocytes	%	$\leq 10$	$\geq 80$
Monocytes	%	Not applicable	$\geq 20$
Basophils	%	Not applicable	$\geq 5$
Bands	%	Not applicable	$\geq 20$
Platelets	$10^9/L$	$\leq 75$	$\geq 700$
Total RBC	$10^{12}/L$	$\leq 3.5$	Not applicable
Clinical Chemistry			
AST	IU/L	Not applicable	$> 3 \times \text{ULN}$
ALT	IU/L	Not applicable	$> 3 \times \text{ULN}$
Alkaline phosphatase	IU/L	Not applicable	$> 3 \times \text{ULN}$ and 25% increase from baseline
GGT	IU/L	Not applicable	$> 3 \times \text{ULN}$
LDH	IU/L	Not applicable	$> 3 \times \text{ULN}$
Total bilirubin	$\mu\text{mol}/L$	Not applicable	$\geq 1.5 \times \text{ULN}$
Urea nitrogen	mmol/L	Not applicable	$\geq 10.7$
Creatinine	$\mu\text{mol}/L$	Not applicable	$\geq 177$
Total protein	g/L	$\leq 45$	$\geq 90$
Albumin	g/L	$\leq 25$	$\geq 65$
Sodium	mmol/L	$\leq 130$	$\geq 155$
Potassium	mmol/L	$\leq 3.0$	$\geq 5.8$
Chloride	mmol/L	$\leq 90$	$\geq 115$
Phosphorus	mmol/L	$\leq 0.5$	$\geq 1.9$
Calcium	mmol/L	$\leq 1.8$	$\geq 3.9$
Uric acid	mmol/L	Not applicable	$\geq 0.62$
Glucose	mmol/L	$\leq 2.8$	$\geq 10$
Total cholesterol	mmol/L	Not applicable	$\geq 8.0$
Urinalysis: Quantitative			
pH	None	$\leq 4$	Not applicable
Specific gravity	None	$\leq 1.005$	Not applicable
Urinalysis: Dipstick Chemistries			
Glucose	0 - 4+	Not applicable	Increase of 2 or more units from baseline

Variable	Units	Markedly abnormal Criteria	
		Low	High
Casts		Not applicable	Increase of 2 or more units from baseline
Protein	0 - 4+	Not applicable	Increase of 2 or more units from baseline
Ketones	0 - 4+	Not applicable	Increase of 2 or more units from baseline
Blood (Hgb)	0 - 4+	Not applicable	Increase of 2 or more units from baseline
Urinalysis: Microscopic Variables			
RBC	no./hpf	Not applicable	$\geq 10$
WBC	no./hpf	Not applicable	$\geq 20$
Casts	no./hpf	Not applicable	Neg at baseline to positive on-treatment
Bacteria	no./hpf	Not applicable	Neg at baseline to positive on-treatment
Cells	no./hpf	Not applicable	Neg at baseline to positive on-treatment

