Crystals	no./hpf	Not applicable	Neg at baseline to positive on-treatment

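### SAP 10.3.2 defines the urinalysis categories Absent and Present by whether a value exists, so the shift tables, taken literally, miss every negative-to-positive change

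*SAP*

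**What the plan says.** SAP 10.3.2 lists five categories for laboratory shift tables. Low, Normal and High rest on the reference range. The other two are for urinalysis only:

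- "Absent: No value for measured variable (for urinalysis only")
- "Present: Any value obtained for measured variable (for urinalysis only")

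The same section then states that "shift tables will summarise the number (%) of subjects who had “absent” values at baseline and “present” values during the treatment period". It exempts no urinalysis variable, and it specifies the Low/High shift tables for haematology and chemistry only.

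SAP 10.3.4 says that "incidence of changes in urinalysis will be summarised by treatment group", and adds: "A summary table with number of subjects with change from *Absent* at baseline to *Present* during trial will be summarised". It gives no definition of its own.

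The baseline rule in SAP 10.3 is: "Baseline for all laboratory analyses will be the values obtained at the last assessment prior to the first dose". Neither 10.3.2 nor 10.3.4 says what happens to a subject without a baseline value.

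Appendix 1, Table 2 uses different concepts for the same tests. For microscopic casts, bacteria, cells and crystals the criterion is "Neg at baseline to positive on-treatment". For dipstick glucose, protein, ketones and blood, graded 0 to 4+, it is "Increase of 2 or more units from baseline".

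**The concern.** The two definitions describe whether a result was obtained, not whether the analyte was found. A baseline protein dipstick reported as 0 is a value, so the subject is Present at baseline. If protein later reaches 4+, the subject is still Present and no shift is recorded. A subject whose baseline sample was lost is Absent, and becomes a shift as soon as any later result arrives, including a normal one.

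The table is meant to show, within subjects and by arm, how many developed a urine finding after dosing. Programmed as written it answers another question: how many had no baseline sample. A reader of the report who saw few or no shifts in either arm would take that as evidence of no new urine findings, when the table could not have shown them.

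**Working it through.** The plan states no figure on this point, so there is none to reproduce. The check applies the written rule to every possible result.

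**Inputs.** The definitions and the counted shift come from SAP 10.3.2. The dipstick scale, 0 to 4+, comes from SAP Appendix 1, Table 2. Allowing for a missing result, each assessment has 6 possible states (missing, 0, 1+, 2+, 3+, 4+), which gives 6 × 6 = 36 pairs of baseline and later result.

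**Two classifications of each pair.**

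- As written: missing is Absent, and any of 0 to 4+ is Present.
- Negative/positive: 0 is Absent, 1+ to 4+ is Present, and missing is kept apart.

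| Baseline | Later result | Pairs | As written | Negative/positive |
|---|---|---|---|---|
| missing | 0 | 1 | counted | not counted |
| missing | 1+ to 4+ | 4 | counted | not counted |
| 0 | 1+ to 4+ | 4 | not counted (Present to Present) | counted |
| all others | | 27 | not counted | not counted |

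**Result.** The written rule counts 1 + 4 = 5 of 36 pairs, all with a missing baseline. One of them, missing to 0, ends in a normal result. The negative/positive rule counts 4 of 36, exactly the newly positive pairs. The two rules have no counted pair in common.

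**What the table would show in practice.** Protocol 6.1 and the Trial Assessment Table schedule urinalysis at screening, so few baselines should be missing. For most analytes the literal count would therefore be close to zero in both arms, whatever the urine results were.

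**Urine osmolality is the exception.** Protocol 6.3 and 7.2.3 place it in the urinalysis panel at Visit 3 only, after dosing. It has no baseline, so under the written rule nearly every subject with a Visit 3 result moves from Absent to Present.

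**Reading Absent as none detected.** This repairs graded dipstick and microscopy tests. It does not repair pH and specific gravity, which Table 2 lists as quantitative: a measured pH or specific gravity always has a value, so every subject is Present at every assessment and no shift can occur. It gives osmolality no baseline, and it leaves open whether a trace result is negative or positive.

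**The case against.** The strongest reply is that the intended meaning can be recovered. The section concerns changes relative to a normal range. It speaks of subjects having absent values, which treats absence as a kind of result, and of a measured variable, which a lost sample is not. Appendix 1 uses negative to positive. A programmer may well have coded not detected versus detected, and the table shells are in a separate document (SAP 14) that is not available here. This stands as an account of what the authors probably meant. It does not remove the defect: no sentence of the SAP ties the two categories to a negative or positive result, Appendix 1 contradicts the literal definition instead of supplying another, and pH, specific gravity, osmolality and trace stay unresolved on the kinder reading.

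The second reply concerns reach, and it largely stands. A reader might infer that the trial would have no by-arm view of urinalysis changes. The documents do not support that:

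- SAP 10.3.4 also tabulates urinalysis categories by arm at each scheduled time point.
- SAP 10.3.1 summarises change from baseline for each laboratory variable, which serves numeric ones such as pH and specific gravity.
- SAP 10.3.3 lists abnormal and markedly abnormal values.
- Protocol 7.2.3 asks that clinically significant laboratory abnormalities be reported as adverse events.

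The secondary endpoint is clinically significant change, judged by the investigator, and this shift count is not that endpoint.

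A reader might also infer that the table would carry a sizeable number of false shifts caused by missing baselines. No document gives a missing-baseline rate, and the screening schedule points the other way. Nor would the table read zero throughout if every baseline were complete, because osmolality would still show as shifted. Finally, a subject who goes from missing to positive is an unsupported shift, not a proven false one.

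**Conclusion.** The definitions are wrong as written. This is more than missing detail: a stated rule, followed literally, gives the wrong table. It counts 5 of 36 result pairs, all with a missing baseline, and 0 of the 4 pairs that represent a new positive finding.

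The likely consequence is a nearly empty and falsely reassuring table for most analytes, alongside an osmolality row that shows almost everyone as shifted. This rests on two assumptions: that the SAP is programmed as worded, and that screening urinalysis is done as scheduled. No count of affected subjects can be given from the documents.

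The effect is limited to the descriptive within-subject summary of new qualitative urine findings. Abnormalities would still appear in the other urinalysis tables and listings. Safety is not formally tested (SAP 10.1), and no efficacy conclusion depends on this.

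**What to change.** In SAP 10.3.2:

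1. Define Absent as a reported result of negative, 0 or none seen, and Present as a reported positive result. State how trace is classed, and settle it before unblinding. The documents give no rule for trace, so the sponsor has to choose one.
2. Exclude subjects with a missing baseline or no post-baseline result from the shift denominator, or show them on a separate line.
3. Limit Absent/Present to qualitative tests. Use Low/Normal/High for pH and specific gravity.
4. Summarise urine osmolality at Visit 3 only, with no shift, since it has no baseline.

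Apply the same definitions in SAP 10.3.4.

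The cost is a few lines of SAP text and matching changes to programs and shells. Low/Normal/High for pH and specific gravity needs the central laboratory's reference limits. No new data are needed and the design does not change.
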